Development and Evaluation of a Psychomotor Rehabilitation Nursing Plan for the Elderly with Mild Cognitive Impairment to Promote Cognitive Health

Research Proposal

February 2025

Protocol ID: JZMULL2025230

Ethics Approval Number: USM/JEPeM/PP/24090806

Exclusive summary of research proposal (max 300)

(Include the problem statement, objectives, research methodology, expected output/ outcomes/ implication, significance of output from the research project)

With the aging of the population, the number of older adults with mild cognitive impairment (MCI) has increased year by year, which has caused serious social and family burdens. At present, the existing drug treatment effect is limited. Studies show the application value of non-drug treatment in the older adults with mild cognitive impairment. Psychomotor Therapy (PMT) is now widely used in European countries and has formed an independent scientific system. Therefore, this topic pays attention to older adults with mild cognitive impairment, intending to promote cognitive stimulation, using PMT methods to build a rehabilitation nursing plan. Relying on older adults care institutions, older adults with mild cognitive impairment in a certain period were divided into a control group (CG) and an experimental group (EG). Older adults will be engaged in a 12-week PMT rehabilitation nursing plan involving relaxation and breathing exercises, face exercises, hand exercises, and mind exercises to promote cognitive health. SPSS 28.0 software was used to analyze data. The comparison of scores of various scales are based on paired t-test statistical methods. The P value <0.05 will be considered to indicate statistically significant with 95% confidence interval (CI). The rehabilitation effect of the two groups was evaluated according to cognitive assessments (Montreal Cognitive Assessment, MoCA), psychological assessment (Positive and Negative Syndrome Scale, PANSS), and emotional assessment (Hamilton Depression Rating Scale, HAMD-17; Hamilton Anxiety Rating Scale, HAMA-14) . The expected findings of this study may be useful for cognitive rehabilitation plans for the elderly in care institutions, rehabilitation hospitals, communities, and families.

Introduction

Research background

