1) Research design: Quasi-Experimental Design (Non-randomized controlled trial) with experiment and control groups for comparison. Because of ethical considerations on older adults for logistical and economical wise, easy to travel, practical, less budget. Similar studies involving rehabilitation or behavioural interventions in real-world settings have widely used quasi-experimental designs. Studies by MA Handley(2018) and AD Harris (2006) demonstrated reliable outcomes using this approach.

2) Study area: Liaoning Province, China.

3) Study population

i) Reference population: Older adults living in Liaoning.

ii) Source population / sampling pool: Elderly care institutions and rehabilitation centers, Liaoning Province.

iii) Target population: Jinzhou Comprehensive Elderly Care Institution and Rehabilitation Center, Liaoning Province.

iv) Sampling frame: List of members from the two elderly care institution and rehabilitation center; Jinzhou Pension Comprehensive Service Center (JPCSC)), and Jinzhou Rehabilitation Hospital (JRH), Liaoning Province.

4) Subject criteria

Objective No. 1 and 2: To develop and validate the psychomotor rehabilitation nursing plan through content/face validation using the Delphi method.

Inclusion criteria:

- i) Professionals with ≥ 5 years of experience in geriatric care, neurological rehabilitation, cognitive rehabilitation, or psychomotor therapy.
- ii) Academic researchers with publications in related fields.
- iii) Intermediate professional title or above.
- iv) Willingness to participate in multiple Delphi rounds and provide informed feedback.

Exclusion criteria:

- i) Experts without sufficient relevant experience.
- ii) Those unable to commit to the Delphi process.

Objective No. 3: To evaluate the effectiveness of the psychomotor rehabilitation nursing plan in enhancing cognitive function among older adults with mild cognitive impairment. (Experimental and control group)

Inclusion criteria:

- i) Older adults are aged 50 years and above.
- ii) Subjective cognitive complaints from the individual or caregiver.
- iii) Screening for MCI using the Mini-Cog scores between 0-2 (SN Abayomi, 2024).
- iv) Basic language communication, listening, speaking, and understanding skills.

- v) Ability to provide informed consent.

Exclusion criteria:

- i) Diagnosed with severe psychiatric conditions (e.g., schizophrenia, major depressive disorder).

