- ii) It is at the end stage of important functional organ diseases, such as malignant tumors, cardiac failure, etc.
- iii) Limb dysfunction.
- iv) Diagnosed with dementia.

Withdrawal criteria:

- i) Withdrawal of consent by the participant.
- ii) Non-compliance with study requirements (e.g., missing >25% sessions).
- iii) Significant health deterioration affecting participation.

5) Study groups

Experimental group: Older adults with MCI from Jinzhou Rehabilitation Hospital (JRH), with psychomotor rehabilitation nursing plan.

Control group: Older adults with MCI from Jinzhou Pension Comprehensive Service Center (JPCSC), without psychomotor rehabilitation nursing plan.

6) Operational definition:

- i) Mild cognitive impairment (MCI): Mild Cognitive Impairment (MCI) is defined as a condition characterized by noticeable cognitive decline beyond what is expected for an individual's age and education level, but not severe enough to interfere significantly with daily life or independent functioning. It serves as an intermediate stage between normal aging and dementia. (Petersen, R.C., 2004; B. Winblad, 2004).
- ii) Psychomotor therapy (PMT): Psychomotor therapy is a form of therapeutic intervention that focuses on the connection between psychological and motor (physical) functions (Duan Zhouying, Chen Wenhua, 2021).

7) Sample size determination

Objective No. 1 and 2: To develop and validate the psychomotor rehabilitation nursing plan through content/face validation using the Delphi method for older adults with mild cognitive impairment in promoting cognitive function.

A sample size of 8 to 15 respondents has been recommended for Delphi studies, given that smaller samples reduce reliability and bigger ones do not appear to add much value (Kenney et al., 2010). For this study, we aimed to recruit 10-12 participants.

Objective No. 3: To determine the effectiveness of the psychomotor rehabilitation nursing plan in enhancing cognitive function among older adults with mild cognitive impairment .

The sample size was calculated for specific objective 2. It was estimated by using the sample size formula compared with the average of two samples (Ni Ping et al., 2010) . The sample size calculation formula and parameters were as below:

$$N1 = N2 = 2[(t_{\alpha/2} + t_{\beta})S/\delta]^2$$

N1 is the sample content of the experimental group.

N2 is the sample content of the control group.

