S is the estimated value of the standard deviation between the two populations.

δ is the difference between the two averages.

The S and δ were the values of the MMSE scale decided by the researcher based on expert opinion (Liang Jingzhao, Zhi Yanmin, 2022), S= 2.75 , δ = 2.14. The level of significance (α) was 0.05, $t_{0.05/2}= 1.96$, β was 0.10, $t_{0.1}= 1.28$. By substituting the formula, 34 samples were required for each of the two groups.

An estimated 10% was added to the calculated sample size in anticipation of some missing data. The calculated sample size for this study was 76 patients (EG: 38 patients, CG: 38 patients).

8) Sampling method: Purposive sampling

9) Subject setting and participant

PHASE 1 (Delphi-method study for screening and recruitment)

The psychomotor rehabilitation nursing plan design will use Delphi-method which is an integration involving multiple expertise for the PMT development. The participants are the professionals with academic and/or practical experience in Neurology and cognitive training in China's hospitals or universities. There is no agreed method to consider someone an expert in a given field. To facilitate the selection process, it will use a simple point evaluation system. It will include all professionals with a final evaluation of at least 2 points. Regarding academic experience, it will consider the following factors: At least one publication on the

field of cognitive training (1 point) & at least one publication on the field of Neurology (1 point) OR at least one publication on the field of cognitive training in MCI (2 points). Concerning practical experience, it will consider experience in the development of a cognitive training program (1 point). Moreover, it will also consider if the professional had clinical experience in the application of cognitive training (1 point).

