Purposive sampling. Potential participants will be identified through a literature review, existing academic contacts, and a web search for cognitive training programs (for MCI or Neurology or other conditions) and the respective scientific teams. After being evaluated in accordance to the point system previously described, professionals who met the inclusion criteria (2 points or more) will be invited to participate by email. In the initial questionnaire, they will be asked to recommend other professionals who they considered to be experts in the field. Recommended professionals who met the inclusion criteria will be contacted and invited to join the expert panel.

PHASE 2 (Quasi-Experimental design for PMT rehabilitation nursing interventional study)

This experimental method will be used in Quasi-Experimental Design (Non-randomized controlled trial) with experiment and control groups for comparison. Ethics consideration on older adults which would psychologically and emotionally impact in case not selected for experimental group. This research will be carried out in Liaoning Province of China. The rehabilitation nursing intervention will be carried out for older adults with MCI admitted in two China elderly care institutions which the name is Jinzhou Pension Comprehensive Service Center (JPCSC) and Jinzhou Rehabilitation Hospital (JRH). Because of ethical consideration on older adults for logistical and economical wise, easy to travel, practical, less budget. So the experimental group is JRH, and the control group is JPCSC. Purposive sampling, whereby older adults with MCI will be selected and invited to participate the study.

The PMT rehabilitation nursing intervention plan

From Table in the literature review, we can see that most interventions lasted for 3 months. Therefore, older adults will be engaged in a 12-week PMT rehabilitation nursing plan involving 2 phases of relaxation and breathing exercises, face exercises, hand exercises and mind exercises to promote cognitive health. The experimental group will be given interventions, twice a week every Tuesday and Thursday 9-10 am along with the study

intervention. Meanwhile, the control group will be given a standard health education on cognitive health.

Table The Mind-body Exercise of Psychomotor Rehabilitation Nursing Plan

Week	Phase	Intervention methods	Assessment

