2.6 Phase 2 -Task 1	Do relaxation and breathing exercises before and after exercise (10 minutes).			
2.7 Phase 2 -Task 2	Hand muscle training/flexibility training/hand-eye coordination/improved circulation: The older adults held and rotated two balls with one hand according to instructions (10 minutes).			
2.8 Phase 2 -Task 3	Hand fine training/flexibility training/hand-eye coordination/endurance and concentration training (10 minutes).			
2.9 Phase 2 -Task 4	Hand-eye coordination training/cognitive ability training/fine skills training/teamwork and social interaction training (10 minutes).			
2.10 Phase 2 -Task 5	Carry out upper limb gymnastics exercises with music to improve limb motor function (20 minutes).			

Objective No. 3: To evaluate the effectiveness of psychomotor rehabilitation nursing plan in enhancing cognitive function among older adults with mild cognitive impairment.

Data entry and analysis will be performed using SPSS 28.0 software. Descriptive statistics will be used to summarize the general information of older adults. Numerical data will be presented as mean (SD) or median (IQR) based on their normality distribution. Categorical data will be presented as frequency (%). The comparison of scores of various scales are based on paired t-test statistical methods. The P value <0.05 will be considered to indicate statistically significant with 95% confidence interval (CI).

Expected result (Dummy Table): The effect assessment of the PMT rehabilitation nursing plan

Table Comparison of cognitive status between two groups ($\bar{x} \pm s$, scores)

Assessment	Before (n = 76)	After (n = 76)	Diff (95% CI)	t	P
Orientation					
Registration					
Attention and Calculation					
Recall					
Language and Praxis					
MoCA total score					

[figure not shown]
Table Comparison of psychological status between two groups ($\bar{x} \pm s$, scores)

Assessment	Before (n = 76)	After (n = 76)	Diff (95% CI)	t	P
Positive scale					
General psychopathology scale					
Negative scale					

Table Comparison of mental rehabilitation status between two groups ($\bar{x} \pm s$, scores)

Assessment	Before (n = 76)	After (n = 76)	Diff (95% CI)	t	P
Mood-related signs					
Behavioral disturbance					
Cyclic functions					
Ideational disturbance					

Study flowchart

Gantt chart & milestone

Research Activities	2024				2025				2026			
	Jan-Mar	Apr-Jun	Jul-Sep	Oct-Dec	Jan-Mar	Apr-Jun	Jul-Sep	Oct-Dec	Jan-Mar	Apr-Jun	Jul-Sep	Oct-Dec
Preliminary discussion												

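### Objective 3 is a two-group question, but the only planned test is a paired t-test in pooled before/after tables, so no experimental-versus-control effect is ever estimated

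*Combined protocol and SAP*

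**What the plan says.** Methodology section 1 describes a "Quasi-Experimental Design (Non-randomized controlled trial) with experiment and control groups for comparison". Section 5 and Phase 2 of section 9 assign the groups by institution: "So the experimental group is JRH, and the control group is JPCSC". The executive summary says that "The rehabilitation effect of the two groups was evaluated according to cognitive assessments" and the other scales.

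Section 7 sizes Objective 3 with a two-sample formula: "It was estimated by using the sample size formula compared with the average of two samples". The result is stated as "The calculated sample size for this study was 76 patients (EG: 38 patients, CG: 38 patients"). S = 2.75 and δ = 2.14 "were the values of the MMSE scale decided by the researcher based on expert opinion".

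The Objective 3 part of section 11, after descriptive statistics, names a single test, and the summary repeats the sentence: "The comparison of scores of various scales are based on paired t-test statistical methods". The expected-result tables follow. The first is titled "Comparison of cognitive status between two groups", and the psychological and mental-rehabilitation tables have parallel titles. All three have the same columns: Before (n = 76), After (n = 76), the difference with 95% CI, t and P.

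**The concern.** A paired t-test compares two measurements on the same person. It cannot compare people at one institution with people at another. The titles promise a between-group result, but the tables have no cell to hold one.

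There are two ways to read the plan, and neither answers the effectiveness question:

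- **Pooled, as the tables are drawn.** All 76 people enter one before/after test. Any PMT effect is averaged with the control group's change, and a practice gain shared by both groups shows up as a finding.
- **Within each group, if n = 76 is a slip.** The report would contain two P values, and a significant result in the experimental group beside a non-significant one in the control group would be taken as the effect. The difference between groups would have neither an estimate nor an interval.

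Either way the control group has no inferential role in the only effectiveness objective.

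**Working it through.** **Step 1: what the sample size was built for.** Section 7 gives S = 2.75, δ = 2.14, and normal quantiles 1.96 and 1.28.

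n per group = 2[(1.96 + 1.28) × 2.75 / 2.14]² = 2 × 4.1636² = 34.67, stated as 34. Adding 10% gives 34 × 1.10 = 37.4, rounded up to 38, so 76 in total. The figure therefore comes from a two-sided comparison of two independent means. (Rounding 34.67 down rather than up is a separate, minor point.)

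**Step 2: what the planned table would report.** With 38 per group, the pooled difference is

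(38 × experimental change + 38 × control change) / 76 = the average of the two changes.

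This identity needs no assumed SD or correlation. If controls do not change and the experimental group gains 2.14, the table shows (2.14 + 0)/2 = 1.07. If the groups move +1.07 and −1.07, a true difference of 2.14, the table shows 0.

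**Step 3: how often the paired test is significant with no PMT effect (illustration).** Assumptions: S = 2.75, an MMSE value, is carried over to MoCA as the cross-sectional SD; r is the correlation between baseline and 12 weeks; both groups have the same retest gain. The documents give neither r nor a gain. The SD of change is 2.75 × √[2(1 − r)], and rejection rates come from the noncentral t at two-sided 5%.

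| | r = 0.3 | r = 0.5 | r = 0.7 |
|---|---|---|---|
| SD of change | 3.25 | 2.75 | 2.13 |
| Pooled n = 76, gain 0.25 | 10% | 12% | 17% |
| Pooled n = 76, gain 0.5 | 26% | 35% | 52% |
| Pooled n = 76, gain 1 | 75% | 88% | 98% |
| One group n = 38, gain 1 (p) | 45% | 59% | 80% |
| Experimental significant, control not: p(1 − p) | 25% | 24% | 16% |

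With zero gain the pooled test rejects in 5%. In simulation (20,000 runs, 38 per group), a between-group test of change rejects in about 5% under the common 1-point gain.

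**Step 4: whether the planned sample supports a between-group test.** The true difference is 2.14.

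| Two-sample test of change | r = 0.3 | r = 0.5 | r = 0.7 |
|---|---|---|---|
| 38 per group | 81% | 92% | 99% |
| 34 per group (after the 10% loss allowed for) | 76% | 89% | 98% |

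ANCOVA on baseline, with groups alike at baseline and 38 per group, has power of 94%, 97% and 99.7% respectively.

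**Step 5: how each between-group model behaves if the sites differ at baseline.** There is no PMT effect, and a 2-point baseline difference is assumed. Pairs are r = 0.5 and r = 0.7, from the same simulations.

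- *Stable site difference.* The change score estimates 0 and rejects in 5% and 5%. ANCOVA estimates 1.0 and 0.6 and rejects in 39% and 23%.
- *Baseline difference that regresses to a common mean.* ANCOVA estimates 0 and rejects in 5% and 5%. The change score estimates −1.0 and −0.6 and rejects in 35% and 23%.

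**The case against.** The charitable reading is that n = 76 is a template slip, that paired tests would be run by group, and that the table titles show a between-group comparison was intended. This explains the layout but supplies no method: n would then be 38, and a between-group test still appears nowhere in the legible text or tables. The study flowchart and a figure among the tables are not visible in the text reviewed, so the finding is limited to what can be read. Nothing suggests that either names another test.

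Other points have more weight.

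- The rejection rates in step 3 rest on an assumed r and retest gain. They are illustrations, and the finding does not depend on them. The 1.07 also depends on flat controls, although controls do receive health education.
- A between-group change test is not safe in every case. With purposive sampling from two unlike institutions, its false rejection rate can reach the 23% to 35% in step 5. Nothing in the documents settles whether change score or ANCOVA should come first.
- The power margin is thinner than the figures at 38 per group suggest. At 34 analysed and r = 0.3, the change test has 76%, well under the planned 90%. With S read as a cross-sectional SD, the sample-size formula directly sizes a comparison of 12-week scores, and coincides with a change-score test only at r = 0.5.
- Section 10 describes surveys before and after the intervention without naming the groups. That both are measured twice is inferred from n = 76 in the tables.

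These points bear on the choice of model and the caveats. They do not supply the missing contrast.

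**Conclusion.** The concern holds and must be fixed before analysis. The design, the sample size and the table titles all describe a two-group comparison, while the only stated test and every outcome table describe a before/after comparison. On neither reading does the plan produce an experimental-minus-control estimate, so it cannot answer Objective 3.

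The part that rests on least is the averaging: with equal numbers the pooled difference is the mean of the two groups' changes, which halves a 2.14-point effect when controls are flat. The illustrative rates show that the consequence need not be small. Under a shared retest gain of 0.5 point and no PMT effect, the pooled test would be significant in 35% to 52% of trials for r = 0.5 to 0.7, and in 26% at r = 0.3.

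**What to change.** In section 11 and the summary, replace the paired t-test as the effectiveness test with a pre-specified between-group comparison: change in MoCA total from baseline to 12 weeks, experimental minus control, with 95% CI and P. Adjust it for a short list of baseline variables already on the data collection form, such as age and education level. Report ANCOVA with baseline MoCA as a sensitivity analysis, and say in advance that the two models can disagree if the sites differ at baseline and why (step 5). The order of the two models is a judgement; the contrast itself is the requirement. Treat PANSS, HAMD-17 and HAMA-14 the same way.

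Redraw the tables with experimental and control columns (planned 38 each, actual number analysed shown), before and after values, and the between-group difference. Use row labels that belong to the scales collected. Keep paired within-group changes as description only. Confirm in section 10 that both groups are assessed at both times. State that, because group and institution coincide and allocation is not randomized, no adjustment can separate a PMT effect from a site effect.

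The cost is rewording, redrawn tables and one or two models per scale, with no new data if both groups are measured twice as the tables imply. The drawback is some loss of power for the change score against ANCOVA when the sites are alike at baseline: with 38 per group, 92% against 97% at r = 0.5, and 81% against 94% at r = 0.3.

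### Section 11 names no primary outcome for Objective 3 and tests every table row at P<0.05, so no identified test carries the effectiveness conclusion or the planned 90% power

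*Combined protocol and SAP*

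**What the plan says.** Section 11, Objective No. 3, has two operative sentences. The test: "The comparison of scores of various scales are based on paired t-test statistical methods". The rule: "The P value <0.05 will be considered to indicate statistically significant with 95% confidence interval (CI". Three dummy tables for the effect assessment follow, each with t and P columns:

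- cognitive status: six rows, of which MoCA total is the last and is not marked out;
- psychological status: three PANSS scales;
- mental rehabilitation status: four rows.

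No row is called primary or secondary. No testing order, adjustment or success criterion appears. The phrase primary outcomes occurs only as a column heading in the literature review table.

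Specific objective 3 is about cognitive function, which is a domain and not an endpoint. The executive summary is broader. It says "The rehabilitation effect of the two groups was evaluated according to cognitive assessments" and then continues with the psychological and emotional scales, so MoCA, PANSS, HAMD-17 and HAMA-14 stand together unranked.

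Section 7 (Sample size determination) takes its inputs from another scale: "The S and δ were the values of the MMSE scale decided by the researcher based on expert opinion", with "S= 2.75 , δ = 2.14", alpha 0.05 and beta 0.10. Section 10 lists the questionnaires given at baseline and 12 weeks. MMSE is not among them.

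**The concern.** A plan that will end in a statement about effectiveness needs to say which test the statement rests on. Here a reader cannot tell. The rule attaches the word significant to each row separately, and nothing says how the rows combine into a conclusion. If the choice is made after the results are known, a nominal 5% test no longer gives a 5% error rate for the conclusion.

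The sample size would normally reveal the intended primary outcome. Here it points to a scale that will not be measured. Its formula compares two independent means, whereas the stated test is paired. Section 7 also ties the calculation to specific objective 2, which in the list of objectives is the content and face validation. The 90% power therefore belongs to no analysis in section 11.

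**Working it through.** **1. The plan's own figure.** Inputs from section 7: S = 2.75, δ = 2.14, 1.96 for two-sided alpha 0.05, 1.28 for beta 0.10.

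N per group = 2[(1.96 + 1.28) × 2.75 / 2.14]² = 2 × (4.1636)² = 34.67.

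The plan gives 34; rounding up would give 35. Adding 10% to 34 gives 37.4, so 38 per group and 76 in total, as stated. The arithmetic is sound to within rounding. What it does not do is refer to an outcome in section 11.

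**2. Number of tests as drawn.** 6 + 3 + 4 = 13 rows, each with t and P.

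**3. Chance of at least one false positive among k tests at 0.05.** If the tests are independent, this is 1 − 0.95^k.

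- Six cognitive rows: 1 − 0.95^6 = 26.5%.
- All 13 rows: 1 − 0.95^13 = 48.7%.

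For two-sided tests with approximately normal statistics, the Šidák inequality makes these upper limits: correlation can only lower them. Section 11 does not state that the tests are two-sided. I infer it from the alpha/2 in section 7.

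**4. Effect of correlation.** The documents give no correlations between rows, so a range is assumed. The check simulated 13 paired t-tests with n = 76, no true change and one common correlation (20,000 replicates):

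| Common correlation | At least one P<0.05 of 13 |
|---|---|
| 0 | 48.6% |
| 0.3 | 41.6% |
| 0.5 | 33.5% |
| 0.7 | 24.5% |

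If MoCA total is made the sum of the five domain rows, the figures fall slightly, to 47.7%, 39.7%, 32.0% and 23.6%.

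**5. Whether the rows can be counted at all.** The dummy rows were compared with the appended instruments.

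- Registration has no scored counterpart on the appended MoCA form, whose immediate-memory section carries no points.
- Attention and Calculation, and Language and Praxis, are not section titles on that form. Its visuospatial/executive, naming and abstraction sections have no row.
- The four mental-rehabilitation rows (mood-related signs, behavioral disturbance, cyclic functions, ideational disturbance) match no component given for HAMD-17 or HAMA-14 in section 10 or the appendices. Those two scales have no rows of their own.

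The final number of tests is therefore uncertain, and 6 and 13 describe only the tables as they now stand.

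**The case against.** The strongest reply is that the plan never says one significant row proves effectiveness. It says only what will be called significant. Objective 3 confines effectiveness to cognitive function, which PANSS and mood rows cannot answer. On that reading at most six rows matter, and MoCA total is the natural one to look at. This stands, and it is why the six-row figure comes first. It does not remove the problem, because MoCA total is still unmarked among its own domains and the summary counts all four instruments as rehabilitation effect.

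A reader might infer that the plan allows a claim on any of 13 tests with a 49% risk of error. The documents do not support this. No such rule is written. The 48.7% needs independence, which cannot hold when a total stands beside its own parts. A reader might also add HAMD-17 and HAMA-14 totals to reach 15 tests and 53.7%. That probably counts the mood domain twice, since correcting the tables would more naturally replace the four mental-rehabilitation rows than add to them.

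A further objection also stands. As drawn, the tests compare before with after in n = 76, and the figures assume no true change over time. Practice or time effects could make rows significant without any treatment effect. That is a separate problem, which an adjustment for multiple tests would not solve.

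Finally, the conceptual framework and study flowchart have no content in the text available here, so a designation made only there cannot be excluded.

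**Conclusion.** The point holds as a gap in specification. Section 11 names no primary outcome and applies P<0.05 unadjusted to every row, and the sample size rests on a scale that is not an outcome. The effectiveness conclusion therefore has no controlled error rate, and the 90% power has no test to belong to.

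Its size depends on a choice the plan leaves open: up to 26.5% if any cognitive row may support the claim, and up to 48.7% if any drawn row may, with about 24% to 42% as an illustration at correlations of 0.7 to 0.3. These rest on two-sided, approximately normal tests, no true change over time, and the tables as drawn. They are not a measured risk of a false claim of effectiveness. The change should be made before outcome data are analysed.

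**What to change.** In section 11:

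- Name MoCA total as the single primary outcome. Test the between-group difference at week 12, adjusted for baseline MoCA by ANCOVA, at two-sided 0.05.
- Base the effectiveness conclusion on that test, and state its limit. Each arm is one institution and allocation is not randomised (sections 1 and 5). Baseline adjustment is needed because a raw week-12 difference would carry baseline differences between the sites, but it does not separate treatment from site.
- Label PANSS, HAMD-17 and HAMA-14 scores as secondary. Use Holm adjustment if significance is to be claimed; otherwise give estimates with 95% confidence intervals.
- Report subscale rows as estimates with 95% confidence intervals and no claim of significance.
- Align the table rows with the instruments actually used.

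In section 7, restate S and δ for MoCA; the documents give neither, so the 90% cannot simply be carried over.

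The cost is a few lines of text and two consequences. Secondary scales need stronger evidence before they can be called significant. The MoCA test becomes a comparison of 38 with 38 in place of a pooled paired test on 76.
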